8.3 Sample and Recruitment

8.3.1 Eligibility Criteria

8.3.1.1 Inclusion Criteria

- Willing and able to provide informed consent;
- Aged 18 years or older;
- User is confident in their ability to speak and understand English at a proficient level;
- Own a mobile device capable of supporting Wysa;
- A valid email address;
- Referred or self-referred to proceed through the standard IAPT care pathway.

8.3.1.2 Exclusion Criteria

- Patients ineligible for the standard IAPT care pathway;
- Patients with previous and current known major mental illness such as Schizophrenia, severe depression, any co-morbid neurological or neuro-psychiatric condition such as epilepsy;
- Patients with current psychosis or a history of psychotic symptoms within the last 6 months
- Patients with suicidal ideation;
- Patients scoring > 15 points on PHQ- 9;
- Patients scoring > 15 points on GAD- 7;
- Patients with significant cognitive disorders;
- Patients with noted neurodevelopmental conditions such as autism or ADHD;
- Patients previously diagnosed with a personality disorder;
- Patients who been under the care of CMHT or a specialised mental health services in the last 2 years;
- Patients who failed IAPT previously;

- Patients with referrals for specialist presentations of pre-existing, diagnosed conditions requiring a specialised assessment beyond the standard clinical pathway;
- Incapable of self-consent;
- In a dependent/unequal relationship with the research or care teams or any PPI representatives.

8.3.2 Sampling

8.3.2.1 Sample Size

Approx 1100 eligible patients are seen per month at the IAPT in the CNWL NHS Foundation Trust. Preliminary work suggests that Wysa is associated with a mean clinical improvement in PHQ-9 of 5.84 (SD6.66) [28]. This study is powered to detect a clinically meaningful effect on the PHQ-9 scale [28]. Based on a SD of 6.6 and a 2:1 recruitment ratio (usual care: intervention) a sample size of 393 would allow detection of a difference in PHQ-9 of at least 2 points, with 80% power. Augmenting the sample size to 480 would allow for 20% attrition, whilst still maintaining sufficient power to detect clinically and statistically meaningful differences with a Type 1 error rate of 0.05. This inflated sample size would also allow for adjustment for stratification variables, gender, age, ethnicity, self-reported antidepressant use, and severity of depression.

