8.5 Data Analysis

8.5.1 Statistical Methods for Primary Outcome

Descriptive statistics will be used to characterise users, assess baseline comparability, and compare side effects. Primary comparisons between intervention and control groups will be conducted for primary and secondary outcomes. Primary analyses are designed with 80% power to detect a two-sided α of 0.05. All analyses will report 95% CI around estimate of effect. Comparative analyses will be conducted on an intention to treat basis, using linear or logistic regression, with adjustment for stratification variables.

We will explore missingness in our data, be that in relation to primary outcomes, follow-up data and in WYSA analytic information. The proportion of missing data will be explored and reported on descriptively. An hypothesised scenario, where patients remove themselves from the waiting list for treatment before the duration of follow-up may lead to missing data scenario. Currently, estimates

suggest that xxx% of our cohort will 'drop-off' waiting list before our primary endpoint. We will conduct exploratory sensitivity analyses in a complete case ('per protocol') cohort compared with the ITT analysis.

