9.8 Stopping Guidelines

The study monitoring group will review the interim data for consideration of stopping the study early. Given that the estimated sample size is close to the minimum required for adequate power, the study will not be stopped early on the basis of efficacy or benefit. If the monitoring committee identifies any risks that have not been foreseen and mitigated against, the study will be paused while those risks are assessed.

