Real World Testing of an Artificial Intelligence-enabled App as an Early Intervention and
Support Tool in the Mental Health Referral Care Pathway

NCT05533190

8 August 2023

Methods

Randomisation – sequence generation

Demographic data was collected from all patients immediately after completion of the informed consent process, over the phone. Together with data from the IAPT referral, this information was used in the randomisation algorithm to ensure that the intervention and control arms were balanced on key variables (gender, age, ethnicity, self-reported antidepressant use, and severity of depression).

Randomisation – allocation concealment mechanism

Consenting participants were inputted into a masked computer randomisation algorithm and the outcome was recorded in an electronic record to conceal treatment allocation from study researchers. Participants were sent an automatic email to inform them of their group assignment, and participants in the intervention arm will receive the link to download Wysa.

Randomisation – implementation

Psychology assistants recruited specifically for the trial and covering the three London Community Living Well Service sites enrolled participants in the study. A computer generated the random allocation sequence assigned participants to interventions, with a ration of 2:1 randomization to the intervention group.

Blinding

Due to the nature of the intervention, no blinding of participants was possible in the study, as all participants knew whether they were using the app. Clinical treatment teams were not blinded as they knew through the electronic patient record if a participant has received the intervention. The evaluation team will be blinded to treatment using the randomisation algorithm.

Statistical methods

Descriptive statistics was used to assess baseline comparability and the distributions of the primary and secondary outcomes. Visualisations via density and box plots supplemented the tabulations. Linear regression was used to carry out comparative analysis of the primary outcome PHQ9, and secondary outcome GAD7, to compare the two treatment arms. For the primary outcome, PHQ9, the study was powered to detect a clinical meaningful difference of 2 points, with 80% power and a Type 1 error rate of 0.05. Additional post hoc regression was carried out for individuals who had a PHQ2<5 and PHQ2<4 at baseline.

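### Minor: the sample-size figures in Protocol 8.3.2.1 do not agree with each other. 480 covers about 18% attrition from the stated 393, not 20%, and 393 is not the number that the stated SD of 6.6 gives.

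*Protocol*

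**What the plan says.** Protocol 8.3.2.1 first cites preliminary work with a PHQ-9 SD of 6.66. It then describes its own calculation as "Based on a SD of 6.6 and a 2:1 recruitment ratio (usual care: intervention"), and concludes that "a sample size of 393 would allow detection of a difference in PHQ-9 of at least 2 points, with 80% power". The next sentence inflates that number: "Augmenting the sample size to 480 would allow for 20% attrition, whilst still maintaining sufficient power". It gives the error rate as "with a Type 1 error rate of 0.05" and adds that the larger sample also leaves room to adjust for the stratification variables, which include severity of depression.

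Protocol 8.5.1 makes the test two-sided and repeats the power target: "Primary analyses are designed with 80% power to detect a two-sided α of 0.05". It plans regression adjusted for the stratification variables.

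Protocol 9.8 relies on the size of the sample when it rules out early stopping for benefit: "Given that the estimated sample size is close to the minimum required for adequate power".

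The SAP, under Statistical methods, restates the design: "the study was powered to detect a clinical meaningful difference of 2 points, with 80% power and a Type 1 error rate of 0.05". It does not mention attrition.

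**The concern.** Two adjacent sentences give a required number and an enrolment target that is meant to protect it against 20% loss. The natural reading is that 393 would remain after that loss. Simple subtraction shows that they would not. The section also prints two SDs, and the one it names for the calculation does not return the number it reports. So no single set of stated inputs leads to both 393 and 480.

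At stake is whether the attrition tolerance and the 80% power can be taken at face value. Both are headline planning figures, and the documents give no source for the 20%. Anyone checking recruitment or retention against the plan needs to know which number must be analysed and how much loss 480 can absorb.

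**Working it through.** **Inputs.** Difference 2 points, 80% power, SD 6.6 (named for the calculation) or 6.66 (preliminary work), 2:1 allocation, all from Protocol 8.3.2.1; two-sided alpha 0.05 from 8.5.1. The Protocol and SAP give the 2:1 ratio in opposite directions. Power for a given total under even loss is the same either way.

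**Step 1: reproduce 393.** For two means at 2:1, the smaller arm needs n = 1.5 × (1.960 + 0.842)² × SD² / 2².

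- SD 6.66: n = 130.6, rounded up to 131; total 131 + 262 = 393. This is the stated figure.
- SD 6.6: n = 128.2, rounded up to 129; total 129 + 258 = 387. Before rounding, the total is 384.6.

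Other readings do not explain 393: a one-sided test gives 303 to 309, and 1:1 allocation gives 342 to 350. That 393 was computed with 6.66 and reported beside 6.6 is an inference; the documents do not say.

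**Step 2: attrition.**

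- Left after 20% loss: 480 × 0.80 = 384, and 393 − 384 = 9.
- Loss that 480 can absorb: 1 − 393/480 = 18.1%, or 1 − 387/480 = 19.4%.
- Enrolment that covers 20%: 393/0.80 = 491.25, so 492; or 387/0.80 = 483.75, so 484.

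**Step 3: unadjusted power for 2 points.** The standard error is SD × √(1/n₁ + 1/n₂).

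| Analysed | SD | Normal approximation | Noncentral t |
|---|---|---|---|
| 131 + 262 = 393 | 6.6 | 80.8% | 80.6% |
| 131 + 262 = 393 | 6.66 | 80.1% | 79.9% |
| 128 + 256 = 384 | 6.6 | 79.9% | 79.7% |
| 128 + 256 = 384 | 6.66 | 79.2% | 79.0% |

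Going from 393 to 384 costs about 0.9 percentage points. At 384 the shortfall from 80% is 0.1 to 1.0 points, depending on SD and method.

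**Step 4: covariate adjustment.** Adjusting for a covariate with correlation r to the outcome multiplies the SD by √(1 − r²). The documents give no r, so these are assumptions. At 128 + 256 by noncentral t:

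| Assumed r | SD 6.6 | SD 6.66 |
|---|---|---|
| 0.1 | 80.1% | 79.4% |
| 0.2 | 81.3% | 80.6% |
| 0.3 | 83.3% | 82.7% |

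**The case against.** The best defence is that the plan is right to within rounding. With the SD that the section names, the unrounded requirement is 384.6, and 480 less 20% misses it by less than one patient. The text claims only sufficient power after attrition and never says that 393 will remain. The choice of method matters nearly as much as the gap: by noncentral t, even 393 with SD 6.66 gives 79.9%. The adjusted analysis in 8.5.1 includes baseline severity of depression and would probably recover the difference.

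Most of this stands, and it is why the point is minor. It does not remove the inconsistency. The protocol states 393, not 384.6, and in whole patients 480 falls short of 20% cover with either SD. The gain from adjustment cannot be credited to the stated calculation, because the protocol gives no correlation and the SAP names no covariates for the primary regression.

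Three stronger readings are tempting, and the documents do not support them.

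- A reader might infer that the trial fails to deliver its 80% power in any meaningful sense. The shortfall is at most about one point before adjustment.
- A reader might infer a larger loss of power if dropout falls more heavily on one arm. Neither document gives attrition by arm, so any such figure rests on an invented split.
- A reader might infer that the SAP should replace its 80% with power at the number analysed. The SAP sentence describes the design. Power recalculated after the data are in adds nothing to the confidence intervals that 8.5.1 already requires.

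Section 9.8 is not undermined either: calling the sample close to the minimum is consistent with a thin margin.

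**Conclusion.** The point holds as a minor error of statement in Protocol 8.3.2.1. The 393, the 480, the 20% and the SD of 6.6 cannot all be right together: 480 tolerates 18.1% attrition from 393, or 19.4% from the 387 that SD 6.6 gives. At 20% even attrition, unadjusted power for 2 points is about 79.0% (SD 6.66) to 79.7% (SD 6.6). These figures assume a two-sided test at 0.05, equal SDs in the arms, 2:1 allocation, the same proportion lost from each arm, and no gain from covariates. The subtraction itself needs none of these assumptions. Nothing here calls for a larger trial or a different analysis.

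**What to change.** In Protocol 8.3.2.1, use one SD throughout and restate the sentence in one of two ways:

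- *SD 6.66: 393 required; 480 allows for about 18% attrition.*
- *SD 6.6: 387 required; 480 allows for about 19% attrition.*

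In either case, add that at 20% evenly spread attrition the unadjusted power for a 2-point difference is just under 80%. Leave the SAP's 80% as the design power.

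The cost is a sentence or two in one section, with a stated tolerance slightly less favourable than 20%. Enrolment and analysis do not change.

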8.3.2.2 Sampling Technique

Participants will be randomly allocated to intervention or control groups by a computer algorithm after they have provided informed consent and demographic information. Of this sample, a subset will be selected to participate in a semi-structured interview to collect qualitative data about patients' perceptions of Wysa.

To select this subset, a stratified random sampling technique will be used. Patients will be divided based on demographic characteristics (e.g. gender, age, socio-economic status, and ethnicity). From these subgroups, patients will be randomly selected so that the sample interviewed is representative of the UK population.

8.3.3 Recruitment

8.3.3.1 Participant Identification

Participants who are referred, or refer themselves, to IAPT for mental health support (online or by phone) will be recruited from the three provider sites of the London Community Living Well Service, run by the Central North West London NHS Foundation Trust. The service receives on average 1100 referrals a month. All referrals will be screened by the psychology assistant against exclusion criteria and those eligible for the trial will be provided with information regarding the trial via email (see 13.1 Appendix 1). The psychology assistant will then contact participants to check further exclusion criteria not clear from service referral and to take informed consent. Screening will continue through the first 6 months of the intervention period, and we expect to be able to onboard significantly more individuals than our target sample size. All participants will have access to the Wysa app (including control participants who will receive access following the control period).

8.3.3.2 Consent

Current consent for referral to service is collected through a tick box acceptance of terms during online referral. This states: 'Through completing this form you are consenting to have this information stored confidentially on a secure electronic system separate from your GP's system and for your GP to be informed of your contact with us. By providing these details you are giving consent for us to contact you regarding confidential information'

For the trial, explicit consent for participation will be collected (see 13.2 Appendix 2). When individuals self-refer or are referred to the IAPT, they will be screened against the eligibility criteria. Eligible individuals will be sent a study information sheet and then contacted by phone by a study team member to take informed consent and discuss any questions participants might have. Once the trial has started and users download the app as part of intervention they are asked during onboarding if they still consent to take part of the trial and informed of how to remove their data from the trial should they wish to do so.

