8.4.1.2 Allocation Concealment Mechanism

Consenting participants will be inputted into a masked computer randomisation algorithm and the outcome will be recorded in an electronic record to conceal treatment allocation from study researchers. Participants will be sent an automatic email to inform them of their group assignment, and participants in the intervention group will receive the link to download Wysa.

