9.6 Consent

BERA guidelines have been followed for voluntary informed consent, use of methods, and university policies in the event there are issues in delivery [51]. Prior to completing informed consent, participants will be given information that fully describes the process of the study (including the possibility of being randomly selected to be invited to participate in a semi-structured interview), including why their participation is necessary, how their data will be used, and who the results will be reported to. As many patients are understandably concerned about how their data will be used, data management will be explained in detail as part of the consent process. It will also make clear their right to withdraw from the study at any time and have their data destroyed. Patients will also be asked to separately consent for their data to be used to further studies. Declining to share this conversation data will not affect patients' participation in the study or their clinical care.

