Each of the study participants will be given a unique identifier. The primary key between unique ID and participant shall be stored securely for reference purposes and provided to the participant so that they can request that their data be withdrawn from the study. This can be requested at any point prior to data aggregation and will result in all of the patient's files and data being destroyed. Data collected in the study will be analysed using the unique identifiers rather than patient names. Data subject consent forms and primary research data will be retained for 10 years following

publication of the final study results. Study participants will have the option to retain their information within the WYSA app for their onward use or to reset their data at the completion of the study.

Follow-up interview sessions shall be audio recorded by [name] and his research team. The interviews will be transcribed by a transcription service with only reference to the unique identifier provided in the audio file for transcription (the audio file will be reviewed by the CI to ensure no identifying information is in the audio recording; if any is provided it will be edited out); the risk of identification of the interview sessions shall be very low due to this measure being taken. The original audio recording will be destroyed following transcription. Only the Academic CIs and their research staff will have access to research data. The transcription service will have access only to interview audio, following the controls previously mentioned.

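### After allocation, app onboarding asks intervention participants whether they still consent to the trial; no matching prompt is described for controls before the three-month PHQ-9, so loss can differ by arm

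*Protocol*

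**What the plan says.** Explicit trial consent is taken by phone (protocol 8.3.3.2), and allocation follows it: "Participants will be randomly allocated to intervention or control groups by a computer algorithm after they have provided informed consent and demographic information" (8.3.2.2). An automatic email then tells people their group, and "participants in the intervention group will receive the link to download Wysa" (8.4.1.2).

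Section 8.3.3.2 adds a second check. Once "users download the app as part of intervention they are asked during onboarding if they still consent to take part of the trial", they are also "informed of how to remove their data from the trial should they wish to do so".

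Controls do get the app in the end, but later: everyone has access, "including control participants who will receive access following the control period" (8.3.3.1). The GP letter (Appendix 4) puts that at three months. The primary PHQ-9 is taken at baseline and at three months (8.2.5.1).

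The general exit right belongs to both arms. Information given before consent explains "their right to withdraw from the study at any time and have their data destroyed" (9.6). Every participant receives the identifier needed to ask for removal, and a request made before data aggregation "will result in all of the patient's files and data being destroyed" (9.7).

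On analysis, 8.5.1 states: "Comparative analyses will be conducted on an intention to treat basis". Missing data are to be described, and the one sensitivity analysis compares complete cases with the intention-to-treat result. The SAP mentions neither intention to treat, withdrawals nor missing data.

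**The concern.** The onboarding question is about staying in the trial, not about using the app. It is put to people who already know their allocation, and as described it reaches only the intervention arm during primary follow-up. A participant who merely does not want the app is invited to leave the study, when declining the app and staying in follow-up would serve both that person and the analysis.

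Intention to treat depends on outcomes for everyone randomised, whatever they did with the app. If a procedure tied to one arm prompts departures, the people left in that arm are no longer the group that was randomised. Where data have also been destroyed, no later imputation or sensitivity analysis can use that person's baseline or outcome. Complete-case analysis omits the same people, so comparing it with the main result would not reveal the problem. At stake is the comparability of the arms on the primary outcome.

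**Working it through.** **1. Who meets the prompt, and when.**

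| Step | Intervention | Control |
|---|---|---|
| Phone consent, before allocation (8.3.2.2, 8.3.3.2) | yes | yes |
| Told of right to withdraw and have data destroyed (9.6, 9.7) | yes | yes |
| Download link at allocation (8.4.1.2) | yes | no |
| Asked again about trial consent, with removal instructions, before the three-month PHQ-9 (8.3.3.2) | those who download | none described |
| App access after three months (8.3.3.1, Appendix 4) | already has it | yes |
| Questionnaires (8.4.3.1) | Wysa app or Qualtrics | Qualtrics |

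The asymmetry lies in the active prompt and its timing, not in the underlying right.

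**2. What follows a refusal.** No section sets this out. Taken at its word, an answer of no to trial consent ends participation. Destruction needs a further removal request (9.7). Nothing says that someone who refuses at onboarding will still be sent the three-month questionnaires. The SPIRIT-AI checklist refers its retention item (18b) to 8.4.3.2, which covers only the qualitative interviews.

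**3. The plan's own sample size.** Inputs from 8.3.2.1 and 8.5.1: difference 2, SD 6.6, 2:1 usual care to intervention, 80% power, two-sided 0.05.

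n(control) = 3 × (1.960 + 0.842)² × SD² / 2², and n(intervention) is half of that.

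- SD 6.6: 257 + 129 = 386.
- SD 6.66 (the preliminary SD quoted in 8.3.2.1): 262 + 131 = 393, the stated figure.
- Attrition: 393 / 0.80 = 492 against the stated 480. Conversely, 480 × 0.80 = 384 evaluable, which gives 79.9% power at SD 6.6.

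The 20% allowance is not split by arm, and it leaves no power in reserve.

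**4. Bias.** Let x be the fraction of the whole intervention arm lost through the prompt. Let D be the mean three-month PHQ-9 of those lost minus that of those kept, after covariate adjustment.

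Full-arm mean = (1 − x) × kept + x × lost, so kept − full = −x × D.

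Only downloaders see the screen, so x = (share downloading) × (share of those who leave). D is the adjusted difference because 8.5.1 adjusts for the stratification variables, which include depression severity (8.4.1.1). Neither x nor D is given anywhere, so these are assumed values:

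- x = 5%, D = 2: 0.05 × 2 = 0.1 point, 5% of the 2-point target.
- x = 10%, D = 3: 0.10 × 3 = 0.3 point, 15% of the target.

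If D is positive (those lost would have scored worse), the comparison is shifted towards Wysa. If D is negative, it is shifted against Wysa.

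**5. Power.** This takes extra loss in the intervention arm only, on top of 20% attrition in both arms, with difference 2 and SD 6.6. The protocol gives 2:1 usual care to intervention, whereas the SAP gives 2:1 to the intervention group. Both are shown, and the two documents need to be reconciled.

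| Extra loss (assumed) | Protocol ratio | SAP ratio |
|---|---|---|
| 0% | 79.9% | 79.9% |
| 5% | 78.6% | 79.2% |
| 10% | 77.1% | 78.5% |
| 20% | 73.6% | 76.7% |

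At modest loss the cost in power is small. The main issue is selective loss.

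**The case against.** The strongest reply is that the exposed group is narrow and the serious consequence is voluntary. Only people who download Wysa reach the screen, so they were willing enough to install it. Someone too unwell to bother with the app would not normally see the question. Refusing consent and deleting data are separate acts, and destruction follows only a removal request. All of that stands, and it limits how large the loss is likely to be.

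Four stronger readings are tempting, and the documents do not support them:

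- A reader might infer that only the intervention arm is ever told about data removal. Sections 9.6 and 9.7 inform everyone.
- A reader might infer that answering no erases the record. No section says so.
- A reader might infer that the count of those randomised would be lost. Consent records are kept for ten years (9.7, 9.11) and allocation is held in an electronic record (8.4.1.2). Those provisions sit awkwardly with the destruction wording in 9.7, but a lost count is not shown.
- A reader might infer that the bias favours Wysa. In an unblinded trial with a waitlist control, intervention users who feel better may also leave, and controls told to wait may withdraw too.

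The absence of a control-arm prompt is inferred from the text. Figures 4 and 5, the Qualtrics wording, the information sheet and the consent form were not available to this review, and they could contain a matching step or staged withdrawal options.

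It can also be said that attrition is already allowed for, and that a consent check is reasonable when app data start to flow into the patient record. The attrition allowance protects sample size, not comparability between arms. The second argument supports asking about the app and its data, which the change below keeps.

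**Conclusion.** The point holds as a weakness of design. As written, one arm meets a post-allocation question about leaving the trial before the primary outcome, no equivalent is described for the other arm, and nothing in 8.5.1 or the SAP offsets the loss that could result.

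Its size is not known. The results of 0.1 and 0.3 PHQ-9 point illustrate the formula and are not estimates. Figures as high as 1.0 point, half the target difference, can be produced (20% lost, 5 points apart), but only by pairing two assumed extremes, applying the loss rate to the whole arm when only downloaders are exposed, and ignoring adjustment for severity. Entry is also capped at a PHQ-9 of 15 (8.3.1.2), which limits baseline differences. The SAP names linear regression without listing covariates; if the model were unadjusted, the raw difference would apply instead.

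The conclusion rests on two assumptions: that no matching control-arm prompt exists in material not seen, and that a refusal of trial consent is acted on as withdrawal. It is worth acting on because the remedy is cheap and takes no right from participants.

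**What to change.** - **8.3.3.2:** have onboarding ask only about using the app and sharing app data. Record a refusal as declined app, keep the person in follow-up and still send the three-month questionnaires. If trial consent is to be reconfirmed, do so before randomisation, or in both arms with the same wording and timing.
- **9.6 and 9.7:** separate three choices: stopping the app, stopping questionnaires, and deleting data. Reconcile the destruction wording in 9.7 with the retention of consent records in 9.7 and 9.11. Keep a non-identifying record of arm, date and withdrawn status for everyone randomised.
- **SAP and report:** give onboarding refusals and data deletions by arm.

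The cost is a reworded onboarding screen, matching edits to the information sheet and protocol, and an ethics amendment. Some people who decline the app will receive a follow-up questionnaire. The SAP of 8 August 2023 describes enrolment in the past tense. For participants already onboarded, only follow-up where consent allows and reporting by arm remain available.
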